7.5.2.2 Presence of genotypic resistance

The presence of genotypic resistance and association between genotypic resistance and outcome will be an exploratory endpoint described in a separate report.

7.5.2.3 Viral Kinetics of BKV in Plasma and Urine

The BKV plasma and urine viral load, change from baseline and rate of decrease over time by 1 week, 2 weeks, 4 weeks, 8 weeks, 12 weeks, 16 weeks and 36 weeks will be summarized with descriptive statistics. Missing data at each scheduled post-baseline visit will be imputed using the LOCF approach. The corresponding line plots of the plasma and urine BKV viral load over time will be presented by treatment group and study visit.

All plasma and urine BKV viral load data will be listed by treatment and subject.

7.5.3 Other Efficacy Data

All other efficacy data will be listed by treatment and subject.

7.6 Pharmacokinetic Assessment

All pharmacokinetic analyses will be performed by another vendor and described in a standalone PK analysis plan.

The PK of MAU868 will be assessed by fitting a compartmental model to each subject's full set of data, i.e. data collected over the full course of treatment. The specific model will be determined from the data and will be parameterized in terms of clearance(s) and volume(s) of distribution. Additional parameters such as area under the curve and distribution and/or elimination half-lives will also be estimated. Relationships between PK parameters and subject covariates such as age, gender, weight, etc., will be examined as appropriate.

8 INTERIM ANALYSIS

8.1 First Interim Analysis

Following completion of the 12-week treatment period of Cohort 1, unblinded safety and tolerability data (adverse events, clinical laboratories, vitals/physical exams and ECGs), efficacy data (BKV viral load in the plasma) and PK (MAU868 plasma levels) will be provided in the form of individual subject case data packages and reviewed by the SSRC. The treatment assignment in Cohort 1 will be unblinded; however, these data will not include associated subject or site identifiers. The objectives of this interim analysis/this data review are to evaluate whether four doses MAU868 1350 mg IV administered every 28 days for a total of 4 doses demonstrate:

- safety and tolerability signals compared to placebo
- a decrease in BK plasma viral load compared to placebo
- predicted MAU868 plasma levels

The conclusions from this first interim analysis will be used by the Sponsor to evaluate the safety and efficacy of MAU868 early-on in this first-in-patient study. Unless a significant safety issue related to administration of MAU868 has been identified, the conclusions will have no impact on Cohort 2 or the study's design.

For the first interim analysis, unblinded programmed patient profiles will be provided.

8.2 Second Interim Analysis

Following completion of the 12-week treatment periods for Cohorts 1 and 2, cumulative unblinded programmed data from both cohorts will be reviewed for safety and tolerability (adverse events, clinical laboratories, vitals/physical exams and ECGs), efficacy (BKV viral load in the plasma) and PK (MAU868 plasma levels). The objectives of this second interim analysis are to evaluate whether four doses MAU868 1350 mg IV administered every 28 days for a total of 4 doses or MAU868 6750 mg IV administered as a first dose followed by 3 more doses of MAU868 1350 mg IV administered every 28 days demonstrate:

- safety and tolerability signals compared to placebo
- a decrease in viral load compared to placebo

- predicted MAU868 plasma levels

Based on the SSRC's assessment of safety and tolerability and the sponsor assessment of the safety and tolerability, efficacy and PK conclusions for Cohorts 1 and 2, the dosing regimen for Cohort 3 may be adjusted in dosage and/or duration; however, the dosage and duration for Cohort 3 will not exceed the dose already specified in the protocol. Cohort 3 will not be opened for screening and enrollment this evaluation has been completed.

For the second interim analysis, cumulative unblinded programmed patient profiles will be provided. In addition, the programmed statistical tables and listings for Cohorts 1 and 2 will be presented.

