Cohort 3 will not be opened for screening and enrollment until an evaluation of unblinded safety, efficacy and pharmacokinetics findings from both Cohorts 1 and 2 through the 12-week treatment period has been completed by the Sponsor Study Review Committee SSRC.

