7.3 Treatment Period (Day 1 to Day 84)

If the subject meets all inclusion and exclusion criteria, the subject may then be randomized to receive either MAU868 or placebo. Randomization should occur as soon as possible, but not longer than 10 calendar days, after the local qualifying sample was collected.

Subjects will be randomized to study drug in the ratio of 2:1 (MAU868: placebo).

During the treatment period, subjects will receive MAU868 or placebo approximately every 28 days (every 4 weeks) for 12 weeks (4 doses total). Urine and blood will be monitored for BKV DNA weekly by PCR for the first 6 weeks of treatment and then every other week until completion of treatment and at each follow up visit. During this time, BKV DNA by PCR will be tested at the central laboratory.

During the treatment period, subjects should be seen approximately every 7 days (+/- 3 days) during the first 6 weeks and approximately every 14 days (+/-5 days) for the duration of treatment. Subjects may be seen more often at the Investigator's discretion. Visit dates are determined from the Baseline Visit.

NOTE:

- After the first 4 weeks of treatment, the Investigator may request BK viral load (urine and blood) testing more frequently (e.g., weekly) than mandated by the protocol, if clinically indicated.

- Subjects should continue with the study drug (i.e., MAU868 or placebo) until the last scheduled dose, regardless of documented viremia, need for rescue therapy and/or changes in the subject's immunosuppressive regimen.

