7.3.10 Day 84 (Study Drug Infusion 4)

The following procedures will be performed prior to initiation of the study drug infusion; see Schedule of Events ([Appendix A](#)):

- Review and record adverse events
- Review and record concomitant medications
- Obtain subject weight
- Collect blood (serum and plasma) and urine samples for BK viral load testing, viral resistance, immunogenicity, pharmacokinetics, hematology, clinical chemistry, and urinalysis for analysis at central laboratories

- Perform urine or serum pregnancy test for women of childbearing potential
- Record vital signs, including temperature, blood pressure, heart rate, respiratory rate, and oxygen saturation within approximately 30 minutes prior to the initiation of the infusion
- Perform physical examination

If the subject experienced an infusion reaction during their prior administration of study drug, future infusions should be preceded by use of premedication and decreasing the infusion rate.

The following procedures will be performed **after the initiation of the study drug infusion**; see Schedule of Events ([Appendix A](#)):

- Record vital signs, including temperature, blood pressure, heart rate, respiratory rate, and oxygen saturation approximately every 30 minutes (+/- 10 minutes) after the start of the infusion until at least 2 hours after completing the infusion. Vital signs may also be collected at any time during or after the infusion at the Investigator's discretion.
- Collect blood (serum) for pharmacokinetics within approximately 30 minutes following the completion of the infusion and again within approximately 3 to 6 hours after the end of the infusion
- Perform electrocardiogram (12-lead)
- Review and record adverse events
- Review and record any new concomitant medications

Study Drug Administration

Cohort 1: Study Drug Administration Day 84

The subject will receive their study drug infusion (MAU868 1350 mg or Placebo). The respective infusions will be delivered over at least 60 minutes. Following completion of the infusion (infusion bag completely emptied into the drip chamber) a 25 mL D5W flush is to infuse at the same infusion rate as the dose of IP. Start and stop times will be recorded on the eCRF.

Cohort 2: Study Drug Administration Day 84

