10.8.6 Interim Analysis

Interim Analyses

Following completion of the 12-week treatment period of Cohort 1, unblinded safety and tolerability data (adverse events, clinical laboratories, vitals/physical exams and ECGs), efficacy data (BKV viral load in the plasma) and PK (MAU868 plasma levels) will be reviewed by the Sponsor Study Review Committee (SSRC). The treatment assignment in Cohort 1 will be unblinded; however, these data will not include associated subject or site identifiers. The objectives of this interim analysis are to evaluate whether four doses MAU868 1350 mg IV administered every 28 days for a total of 4 doses demonstrate:

- safety and tolerability signals compared to placebo
- a decrease in BK plasma viral load compared to placebo
- predicted MAU868 plasma levels

The conclusions from this first analysis will be used by the Sponsor to evaluate the safety and efficacy of MAU868 early-on in this first-in-patient study. Unless a significant safety issue related to administration of MAU868 has been identified, the conclusions will have no impact on Cohort 2 or the study's design.

Following completion of the 12-week treatment periods for Cohorts 1 and 2, cumulative unblinded data from both cohorts will be reviewed for safety and tolerability (adverse events, clinical laboratories, vitals/physical exams and ECGs), efficacy (BKV viral load in the plasma) and PK (MAU868 plasma levels). The treatment assignments will be unblinded; however, these data will not include associated subject or site identifiers. The objectives of this second interim analysis are to evaluate whether four doses MAU868 1350 mg IV administered every 28 days for a total of 4 doses or MAU868 6750 mg IV administered as a first dose followed by 3 more doses of MAU868 1350 mg IV administered every 28 days demonstrate:

- safety and tolerability signals compared to placebo
- a decrease in viral load compared to placebo
- predicted MAU868 plasma levels

Based on the SSRC's safety, efficacy and PK conclusions for Cohorts 1 and 2, the dosing regimen for Cohort 3 may be *adjusted* in dosage and/or duration; however, the dosage and duration for Cohort 3 will not exceed the dose already specified in the protocol. Cohort 3 will not be opened for screening and enrollment this evaluation has been completed

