Infusion related reaction	Mild transient reaction; interruption not indicated; intervention not indicated	Therapy or infusion interruption indicated but responds promptly to symptomatic treatment (e.g., antihistamines, NSAIDS, narcotics, IV fluids); prophylactic medications indicated for <=24 hrs	Prolonged (e.g. not rapidly responsive to symptomatic medication and/or brief interruption f infusion); recurrence of symptoms following initial improvement; hospitalization indicated for clinical sequelae	Life-threatening consequences; urgent intervention indicated	Death

Definition: A disorder characterized by adverse reaction to the infusion of pharmacological or biological substances.

CYTOKINE RELEASE SYNDROME:

Injury, poisoning and procedural complications					
CTCAE Term	Grade 1	Grade 2	Grade 3	Grade 4	Grade 5
Cytokine release syndrome	Fever with or without constitutional symptoms	Hypotension responding to fluids; hypoxia responding to <40% O ₂	Hypotension managed with one pressor; hypoxia requiring >40% O ₂	Life-threatening consequences: urgent intervention indicated	Death

Definition: disorder characterized by fever, tachypnea, headache, tachycardia, hypotension, rash, and/or hypoxia caused by the release of cytokines.

Navigational Note: Also consider reporting other organ dysfunctions including neurological toxicities such as: Psychiatric disorders: Hallucinations or Confusion; Nervous system disorders: Seizure, Dysphasia, Tremor, or Headache.

SERUM SICKNESS:

Injury, poisoning and procedural complications					
CTCAE Term	Grade 1	Grade 2	Grade 3	Grade 4	Grade 5
Serum sickness	Asymptomatic; clinical or diagnostic observations only; intervention not indicated	Moderate arthralgia: fever, rash, urticaria, antihistamines indicated	Sever arthralgia or arthritis; extensive rash; steroids or IV fluids indicated	Live-threatening consequences; pressor or ventilatory support indicated	Death

Definition: A disorder characterized by a delayed-type hypersensitivity reaction to foreign proteins derived from an animal serum. It occurs approximately six to twenty-one days following the administration of the foreign antigen. Symptoms include fever, arthralgias, myalgias, skin eruptions, lymphadenopathy, chest marked discomfort and dyspnea.

Navigational Note: -

INVESTIGATIONS:

Injury, poisoning and procedural complications					
CTCAE Term	Grade 1	Grade 2	Grade 3	Grade 4	Grade 5

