8.2.2 Cohorts 1 & 2: Response to Study Treatment

The following efficacy endpoints are included in the second interim analysis and will be assessed by the SSRC for subjects in Cohorts 1 and 2. The analysis will be performed based on the MITT Population and will be repeated on the ITT Population.

- Time (weeks) to decrease of BKV plasma viral load by 1 log;
- Time (weeks) to first decrease of BKV plasma viral load to <LLOQ ;
- Proportion of subjects with ≥ 1 log decrease of BKV plasma viral load by 1 week, 2 weeks, 4 weeks, 8 weeks, and 12 weeks;
- Proportion of subjects with decrease of BKV plasma viral load to <LLOQ by 1 week, 2 weeks, 4 weeks, 8 weeks, and 12 weeks;
- Rate of decrease in BKV plasma viral load by 1 week, 2 weeks, 4 weeks, 8 weeks, and 12 weeks;
- Change in eGFR from baseline to week 12;
- Proportion of subjects with BKV nephropathy through week 12;
- Proportion of subjects with graft failure through week 12;
- Proportion of subjects with acute rejection through week 12;
- Proportion of subjects who have died through week 12.

In the efficacy analyses, pairwise contrasts comparing each of the two active groups to the combined placebo group will be tested. The treatment groups will be 3 levels (i.e. Cohort 1 active group, Cohort 2 active group and combined placebo group). The analyses will be conducted using two sided tests at the alpha=0.05 level of significance, with no adjustment for multiplicity.

The efficacy endpoints above for the second interim analysis will be summarized and analyzed in the same manner as described in Section 7.5.1 with the exception that Cohort 3 subjects will not be included in the interim analysis.

8.2.3 Pharmacokinetics Cohort 1 and 2

MAU868 serum concentrations through Week 16 will be evaluated by the SSRC for both Cohorts 1 and 2. The pharmacokinetic analyses will be performed by another vendor and described in a standalone PK analysis plan.

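### At the second interim, the Week 12 viral-load and eGFR results are taken before the fourth infusion, although the stated objective is to evaluate four-dose regimens

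*SAP*

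**What the plan says.** **Dosing and sampling.** The Schedule of Events (Protocol Appendix A, SAP Table 1) places infusions on Days 1, 28, 56 and 84. Protocol 7.3 bounds the treatment period at Days 1 and 84. For Day 84, Protocol 7.3.10 opens with "The following procedures will be performed prior to initiation of the study drug infusion", and the list under that line includes viral load and clinical chemistry. The next scheduled viral load is at Day 112 (Protocol 7.4.1).

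**The second interim.** SAP 8.2 gives its purpose: "The objectives of this second interim analysis are to evaluate whether four doses MAU868 1350 mg IV administered every 28 days", or the Cohort 2 regimen, show a safety signal, a fall in viral load and the predicted drug levels. The review follows completion of the 12-week treatment periods of Cohorts 1 and 2, and the Cohort 3 dosage or duration may be adjusted as a result.

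**What it looks at.** In SAP 8.2.2 the responder, rate-of-decrease and eGFR endpoints have Week 12 as their last timepoint. Nephropathy, graft failure, rejection and death are also counted to Week 12. The two time-to-event endpoints carry no such limit. SAP 8.2.3 says "MAU868 serum concentrations through Week 16 will be evaluated by the SSRC for both Cohorts 1 and 2". SAP 8.2 and 8.2.1 describe cumulative safety data without a cut-off.

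**The gate.** Protocol 3.1 says "Cohort 3 will not be opened for screening and enrollment until an evaluation of unblinded safety, efficacy and pharmacokinetics findings" from both cohorts has been completed, and limits those findings to the 12-week treatment period. SAP 5 repeats that limit.

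**The concern.** The treatment period ends on the day of the fourth infusion, and that day's laboratory samples come first. A Week 12 viral load or eGFR therefore cannot contain any effect of dose 4. The committee would read it under an objective that speaks of four doses, beside drug concentrations that do cover all four.

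This review may alter the duration of Cohort 3. Shortening a four-dose course raises the question of what happens after the last dose, and the landmark tables as listed are silent on that. SAP 9 records that Week 16 was added to the final-analysis endpoints, but the interim list was not extended to match.

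There is also a safety question. The trigger is completion of the treatment period, and no minimum observation after dose 4 is written down. Protocol Appendix D says of serum sickness: "It occurs approximately six to twenty-one days following the administration of the foreign antigen". For the last subject treated, that window opens only after the trigger.

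**Working it through.** **1. Reproduce the plan's dose count.** Infusions on Days 1, 28, 56 and 84 make 4 doses by the end of Day 84. This agrees with the stated total.

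**2. Doses behind the Week 12 sample.** Infusions before the Day 84 pre-infusion sample are those on Days 1, 28 and 56, so 3 of 4.

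- Cohort 1: 3 × 1350 = 4050 mg of 4 × 1350 = 5400 mg, or 75%.
- Cohort 2: 6750 + 2 × 1350 = 9450 mg of 6750 + 3 × 1350 = 10800 mg, or 87.5%.

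The ±5-day visit window (Day 79 to Day 89) does not change this, because sampling and infusion belong to the same visit.

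**3. Time after dose 4.** At the Week 12 sample it is 0 days. At Week 16 it is 112 − 84 = 28 days.

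**4. Can later data enter a Week 12 result?** No. The responder endpoints use the last observation up to the named timepoint (SAP 7.5.1.4 and 7.5.1.5). Rate of decrease and eGFR use the visit value, with earlier values carried forward if it is missing (SAP 7.5.1.7 and 7.5.1.8).

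**5. The components side by side.**

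| Component of second interim | Stated limit | Coverage of dose 4 |
|---|---|---|
| Responder, rate of decrease, eGFR (SAP 8.2.2) | Week 12 | None |
| Nephropathy, graft failure, rejection, death (SAP 8.2.2) | Week 12 | Almost no time after it |
| Time to 1-log fall, time to <LLOQ (SAP 8.2.2, 7.5.1.1, 7.5.1.2) | None stated | Whatever has accrued |
| Safety (SAP 8.2, 8.2.1) | Cumulative, none stated | Infusion day guaranteed; more where accrued |
| PK (SAP 8.2.3) | Week 16 | All 4 doses plus 28 days |
| Cohort 3 gate (Protocol 3.1, SAP 5) | End of 12-week period | Conflicts with the PK row |

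**6. Safety follow-up at the trigger.** For the last subject, completing treatment guarantees only the Day 84 post-infusion checks: vital signs to at least 2 hours, ECG, adverse events and two PK samples. The serum-sickness window after a Day 84 dose is Day 90 (84 + 6) to Day 105 (84 + 21). A nominal Day 112 cut covers it. A Week 16 visit at the early edge of its ±10-day window would give 102 − 84 = 18 days.

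Earlier subjects are better placed. Cohort 2 opens only after a blinded review about 12 weeks after the 9th Cohort 1 subject is randomized, and Cohort 2 then needs at least 12 weeks of treatment. On schedule, Cohort 1 subjects 1 to 9 are at least 12 + 12 − 12 = 12 weeks past dose 4 at the second interim.

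**The case against.** Several points on the other side are sound, and they rule out stronger readings.

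**Both interims.** Protocol 10.8.6 words the first interim in the same way ("The objectives of this interim analysis are to evaluate whether four doses MAU868 1350 mg IV"), so a reader might infer that both reviews are affected equally. The documents do not support that. The first interim has no effect on Cohort 2 or the design unless a significant safety issue appears. It is a review of patient profiles, with no endpoint list and no Week 12 cut.

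**All efficacy stops at Week 12.** A reader might infer this from SAP 8.2.2. The two time-to-event endpoints are analysed as in SAP 7.5.1, which counts events during the study and censors at the last assessment. Cumulative patient profiles are also supplied.

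**A quarter of infusions unobserved.** With 8 active subjects in each of two cohorts, 16 of 64 infusions are fourth doses, and one might infer that 25% lack safety follow-up. That treats a trigger as a data cut. It overlooks the Day 84 post-infusion checks, the Day 112 visit, the longer follow-up of Cohort 1 and the DSMB's separate review. If the committee waits for everyone's Week 16 PK, it meets about 28 days after each dose 4.

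**Limited decision.** Cohort 3 can be adjusted but may not exceed the protocol's dosage and duration. Results after one, two and three doses (Weeks 4, 8 and 12) do bear on shortening, and the study is an unpowered proof of concept.

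What remains is that the landmark tables show no response after the full regimen named in the objective. Protocol 10 lets the SAP override the protocol on analysis, but that does not settle the conflict over the cut, because SAP 5 and SAP 8.2.3 disagree with each other.

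**Conclusion.** The point holds in this form: at the second interim, the landmark viral-load and eGFR results reflect three of four doses (75% of the planned milligrams in Cohort 1 and 87.5% in Cohort 2). The event endpoints include almost no time after dose 4. The stated objective concerns four doses, and the PK covers four.

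It does not follow that the review as a whole judges only three doses. PK, cumulative safety and the time-to-event endpoints can all extend past dose 4. The safety weakness is narrower: no minimum follow-up is specified, and the exposure falls mainly on subjects enrolled late in Cohort 2.

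The conclusion assumes that subjects receive all doses on schedule and that the Day 84 sampling order is followed. No power or error-rate figure is involved. Week 16 data would not isolate the effect of dose 4 from the passage of time, but they give the first scheduled response after the complete regimen.

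**What to change.** For the second interim only:

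- In SAP 8.2.2, add Week 16 to the landmark endpoints (≥1-log decrease, <LLOQ, rate of decrease, eGFR) and to the event endpoints (nephropathy, graft failure, rejection, death), using the Week 16 definitions already in SAP 7.5.1.
- State one data cut at Week 16 (Day 112) for efficacy, safety and PK in SAP 5, 8.2, 8.2.1 and 8.2.2 and in Protocol 3.1 and 10.8.6. This removes the conflict with SAP 8.2.3 and sets the safety follow-up expected after dose 4.
- Label Week 12 viral-load and eGFR results as taken before the fourth dose.

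Leave the timing of the first interim unchanged.

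**Cost.** SAP wording and a short protocol amendment. Viral load, chemistry and adverse events are already collected at Day 112 (Protocol 7.4.1), so no visit or sample is added. The Cohort 3 decision moves by up to about 4 weeks plus the 10-day visit window if the review would otherwise start before Week 16 PK is available, and by little or nothing if it already waits for that PK.
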